Study Aims and Objectives	
To assess the impact of intermediate-dose anticoagulation compared with prophylactic anticoagulation of critically ill patients with COVID-19 with regards to the composite primary endpoint of being alive and without clinically-relevant venous or arterial thrombotic events at discharge from the ICU (without transfer to palliative care unit/hospice) or at ICU duration (if ICU stay lasted 30 days or longer).
 
Clinically relevant venous or arterial thrombotic events will all be adjudicated and are defined as any of the following:
 
 • Confirmed or treated deep venous thrombosis or pulmonary embolism • Type I myocardial infarction (MI) as confirmed by a combination of biomarkers, electrocardiogram and angiogram • New ischemic stroke • Acute limb ischemia • Actionable line thrombosis requiring escalation of anticoagulation or removal or replacement of the line • CVVH Filter thrombosis requiring escalation of anticoagulation • Other thrombotic events requiring anticoagulation (e.g., intracardiac thrombosis)
Secondary Aims:	
 1. To determine the impact of intermediate-dose anticoagulation compared with prophylactic anticoagulation on the individual components of the primary outcome in the ICU. 2. To determine the impact of intermediate-dose anticoagulation compared with prophylactic anticoagulation on ICU length of stay. 3. To determine the impact of intermediate-dose anticoagulation compared with prophylactic anticoagulation on rates of acute kidney injury and renal recovery in the ICU. 4. To determine the safety of intermediate-dose anticoagulation compared with prophylactic anticoagulation with respect to major bleeding (assessed by BARC criteria, also explored by ISTH and TIMI criteria) in the ICU. 5. To determine the impact of intermediate-dose anticoagulation compared with prophylactic anticoagulation on the individual components of the primary outcome until hospital discharge 6. To determine the impact of intermediate-dose anticoagulation compared with prophylactic anticoagulation on hospital length of stay.

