Intervention /Comparator	
Intervention arm: intermediate-dose anticoagulation
 
 • If stable eGFR ≥ 30 mL/min: enoxaparin 1mg/kg SC daily or unfractionated heparin infusion at 10 units/kg/hour with goal anti-Xa 0.1-0.3 U/mL.¹ • If eGFR <30 mL/min or acute kidney injury (as defined below) or CRRT: Unfractionated heparin infusion at 10 units/kg/hour (minimum 500 units/hour if CRRT) with goal anti-Xa 0.1-0.3 U/mL.² 
Control arm: prophylaxis
 
Prophylactic dose anticoagulation (per CUIMC Guidelines):
 
 • If eGFR ≥ 30 mL/min (stable kidney function): 
 ◦ BMI < 40 kg/m2: Enoxaparin 40 mg SC daily ◦ BMI 40 – 50 kg/m2: Enoxaparin 40 mg SC q12h ◦ BMI > 50 kg/m2: Enoxaparin 60 mg SC q12h • If eGFR < 30 mL/min or acute kidney injury: 
 ◦ 50-120 kg: Unfractionated heparin 5000 units SC q8h ◦ > 120 kg: Unfractionated heparin 7500 units SC q8h 
If CRRT: Unfractionated heparin infusion pre-filter at 500 units/hour

Primary Endpoint	
Primary outcome: Composite of being alive and without clinically-relevant venous or arterial thrombotic events at discharge from ICU (without transfer to another palliative care unit/hospice) or at (if ICU duration lasted 30 days or longer).
 
Clinically relevant venous or arterial thrombotic events will all be adjudicated and are defined as any of the following:
 
 Confirmed or treated deep venous thrombosis or pulmonary embolism Type I myocardial infarction (MI) as confirmed by a combination of biomarkers, electrocardiogram and angiogram New ischemic stroke Acute limb ischemia Actionable line thrombosis requiring escalation of anticoagulation or removal or replacement of the line CVVH Filter thrombosis requiring escalation of anticoagulation Other thrombotic events requiring anticoagulation (e.g., intracardiac thrombosis)

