Study intervention	
 Each cluster will be randomized to one of the two antithrombotic regimens: prophylactic-dose or intermediate dose as described above. The choice of agents will be dependent upon the renal function (at the time of enrollment and every subsequent day). At the onset of study enrollment, clusters including patients admitted within the past 5 days will be randomized. Patients who meet eligibility by screening team will be enrolled. Patient is considered enrolled after a co-investigator has confirmed all inclusion/exclusion criteria have been met. Assessment of appropriateness of anticoagulation dose will occur daily based on the renal function, progressive thrombocytopenia or anemia, or development of another indication for anticoagulation such as new-onset atrial fibrillation, Patients' treatment course will be followed from randomization to hospital discharge or 30 days, whichever happens earlier. Patients will continue with randomization therapy until discharged from the ICU, except in the setting of an adverse event attributed to anticoagulation, developing an event requiring therapeutic anticoagulation, or change in code status to comfort measures. Patients transferred between participating ICUs will remain in the treatment arm assigned at initial randomization. Recommendation will be to continue study treatment if patient transferred to ICUs not participating in the present trial. If the study treatment is changed by the primary treating team in the second ICU, then patient will be evaluated by intention to treat principle. 
Intervention arm: intermediate-dose anticoagulation
 
 If stable eGFR ≥ 30 mL/min: enoxaparin 1mg/kg SC daily¹ If eGFR <30 mL/min or acute kidney injury (as defined below) or CRRT: Unfractionated heparin infusion at 10 units/kg/hour (minimum 500 units/hour if CRRT) with goal anti-Xa 0.1-0.3 U/mL² 
Control arm: Prophylactic dose anticoagulation (per CUIMC Guidelines):
 
 If eGFR ≥ 30 mL/min (stable kidney function): 
 BMI < 40 kg/m²: Enoxaparin 40 mg SC daily BMI 40 – 50 kg/m²: Enoxaparin 40 mg SC q12h BMI > 50 kg/m²: Enoxaparin 60 mg SC q12h If eGFR < 30 mL/min or acute kidney injury: • If eGFR < 30 mL/min or acute kidney injury:

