	
 ○ 50-120 kg: Unfractionated heparin 5000 units SC q8h ○ > 120 kg: Unfractionated heparin 7500 units SC q8h • If CRRT: Unfractionated heparin infusion pre-filter at 500 units/hour
Study assessment and activities	
All anticoagulation medications are standard of care according to discussions between clinician leadership in multiple disciplines and review of treatment protocols from institutions in the region and internationally. Anticoagulants will be ordered through the hospital pharmacy.
 
Patient receiving any anticoagulation are at risk for development of hemorrhage, thrombocytopenia, and in rare cases (overall rate of 0.2%) heparin induced thrombocytopenia (7). Patients who have a bleeding event may have cessation of the administered drug per clinical standard of care, and in some cases may require transfusion of blood products, and additional testing and therapy to identify and treat the source of bleeding. Patients who develop a thrombotic event may have intensification of anticoagulation per clinical standard of care.
 
We will collect all clinical, laboratory and imaging data generated per standard of care throughout the patient's hospitalization. Primary and Secondary endpoints will be assessed at ICU discharge, hospital discharge and 30 days if the patient is still hospitalized.

III. Endpoint Definition

a) Endpoint Reporting Requirements

Safety surveillance and reporting starts as soon as the patient is enrolled in the clinical investigation and will continue until the subject is deceased, the subject concludes participation in the clinical investigation or the subject withdraws from the clinical investigation.
Endpoint data will be collected throughout the time period defined above and will be entered on a CRF.

For the purposes of this investigation the following are reportable endpoints:

Death	
Deep venous thrombosis	Diagnosed on duplex ultrasonography including upper (internal jugular, subclavian, axillary/brachial) and lower extremity (iliac, femoral/popliteal, gastrocnemius, peroneal, posterior tibial) thrombosis
Pulmonary embolism	Diagnosed on CT angiography, V/Q scan, or invasive pulmonary angiography

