Type I myocardial infarction	Detection of a rise and/or fall of cTn values with at least one value above the 99th percentile URL and at least one of the following: symptoms of ischemia, new or presumed new significant ST-segment-T wave (ST-T) changes or new left bundle branch block (LBBB); development of

	pathological Q waves on the ECG; imaging evidence of new loss of viable myocardium or new regional wall motion abnormality; identification of an intracoronary thrombus by angiography or autopsy
Ischemic stroke	Neurological dysfunction caused by focal cerebral, spinal, or retinal infarction based on pathological, imaging, or other objective evidence of cerebral, spinal cord, or retinal focal ischemic injury in a defined vascular distribution; or 2. clinical evidence of cerebral, spinal cord, or retinal focal ischemic injury based on symptoms persisting ≥ 24 hours or until death, and other etiologies excluded. Exclude hemorrhagic infarction.
Acute limb ischemia	Sudden decrease in limb perfusion that threatens limb viability with confirmed arterial obstruction based on duplex ultrasonography or invasive peripheral angiography
Actionable line thrombosis	Arterial or central venous catheter thrombosis that results in removal or replacement of catheter or initiation of therapeutic anticoagulation. Excludes use of indwelling tPA.
CVVH filter thrombosis	Filter thrombosis requiring exchange in order to resume continuous veno-venous hemofiltration (CVVH) or resulting in cessation of CVVH
Other thrombotic events requiring anticoagulation	For example atrial fibrillation, left ventricular thrombus, right ventricular thrombus, etc.
Acute kidney injury	KDIGO criteria: 1. Increase in sCr ≥ 0.3 mg/dL (≥ 26.5 $\mu\text{mol}/\text{L}$) within 48 hours; or 2. Increase in sCr ≥ 1.5 times baseline, which is known or presumed to have occurred within the prior 7 days; or 3. Urine volume < 0.5 mL/kg/h for 6 hours.
Serious bleeding	
 BARC 3 or 5 bleeding (3: decrease in the hemoglobin of > 3 g per deciliter, any transfusion, cardiac tamponade, or intracranial or ocular involvement; 5: fatal)

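### Four components of the primary endpoint carry two different definitions, and no section says which one governs, so the same patient can be scored a success or a failure

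*Combined protocol and SAP*

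**What the plan says.** The lists under Study Aims and Objectives and under Primary Endpoint are presented as the definition of a clinically relevant thrombotic event. Section III, headed Endpoint Definition, gives criteria for the same components but introduces its table as reportable endpoints.

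| Component | Study Aims and Primary Endpoint | Section III |
|---|---|---|
| CVVH filter | "CVVH Filter thrombosis requiring escalation of anticoagulation" | "Filter thrombosis requiring exchange in order to resume continuous veno-venous hemofiltration (CVVH) or resulting in cessation of CVVH" |
| DVT/PE | "Confirmed or treated deep venous thrombosis or pulmonary embolism" | PE: "Diagnosed on CT angiography, V/Q scan, or invasive pulmonary angiography"; DVT: diagnosed on duplex ultrasound |
| Line | "Actionable line thrombosis requiring escalation of anticoagulation or removal or replacement of the line" | "Arterial or central venous catheter thrombosis that results in removal or replacement of catheter or initiation of therapeutic anticoagulation", with an exclusion for indwelling tPA |
| Other | Thrombotic events needing anticoagulation, with intracardiac thrombosis as the example | "For example atrial fibrillation, left ventricular thrombus, right ventricular thrombus, etc" |

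The Study intervention section puts atrial fibrillation in a different class. It lists "development of another indication for anticoagulation such as new-onset atrial fibrillation" among the reasons to reassess the dose each day.

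Section IV (Event Adjudication) sends all suspected components to two blinded physicians working from pre-defined clinical definitions. It does not say where those definitions are. Its named list includes neither filter thrombosis nor other thrombotic events.

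**The concern.** The composite outcome makes each patient good or poor. That classification feeds the success tallies, the lead-of-4 rule, the final selection, the 60-patient analysis, the component secondary endpoints and the blinded look at the pooled event rate in Section VIII. Each reclassified patient moves one tally by one, against a required lead of 4.

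Discordance need not be equal by arm. Whether a patient is treated, or has anticoagulation escalated, is a bedside decision. The documents describe blinding only for the adjudicators, and treatment follows rooms designated by arm. Escalation also depends on the starting intensity, which is what the arms differ in. If the question stays open until results are known, the choice of definition could be made with those results in view.

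**Working it through.** **1. Can the two texts classify one patient differently?** Take a patient alive at ICU discharge with no other event.

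| Case | Primary Endpoint list | Section III |
|---|---|---|
| Filter clots and is exchanged, no escalation | success | failure |
| Filter clots, anticoagulation escalated, no exchange or cessation | failure | success |
| DVT or PE treated without imaging | failure | success |
| Line clot, line kept, escalation short of therapeutic | failure | success |
| New atrial fibrillation needing anticoagulation, no thrombus | success | failure, by its own example |

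The filter criteria cross in both directions, so Section III cannot be read as an elaboration of the list. The MI wording is ambiguous rather than contradictory: the list asks for a combination of biomarkers, ECG and angiogram, and Section III for a troponin change plus any one of several features.

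**2. Does any section settle precedence?** No. Both places use the language of definition, there is no cross-reference, and Section IV cites unnamed definitions.

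**3. Reproduce the plan's figure.** Inputs from Section VIII and Table 1, Scenario 1: p1 = 0.35, p2 = 0.20, first look at 30 per arm, stop at a lead of 4 or more, truncate at 50 per arm.

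- At 60 patients the lead is D = X1 − X2, with X1 ~ Bin(30, 0.35) and X2 ~ Bin(30, 0.20). Stop if |D| ≥ 4.
- Otherwise each further pair moves D by +1 with probability p1(1 − p2) = 0.35 × 0.80 = 0.28, by −1 with probability p2(1 − p1) = 0.20 × 0.65 = 0.13, and by 0 with probability 0.59.
- At truncation the larger tally wins. A tie counts one half.

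The exact result is a probability of correct selection (PCS) of 95.2%, a probability of deciding at 60 of 62.6%, and an expected size of 68.4. Table 1 gives 95.1%, 62.6% and 68.4. The better arm leads by exactly 3 with probability 10.6% and by exactly 4 with probability 11.5%. So in about 22% of trials one reclassified patient, in the right direction, takes the trial across the stopping line.

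**4. Equal reclassification.** Assume a fraction f of successes become failures under the other reading, so p becomes p(1 − f) in both arms. The last two columns score the same patients both ways.

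| f (assumed) | Rates | PCS | Decide at 60 | Expected N | Pooled success | Readings differ on stopping at 60 | Opposite arms chosen (ties excluded) |
|---|---|---|---|---|---|---|---|
| 0 | 0.350 / 0.200 | 95.2% | 62.6% | 68.4 | 27.5% | – | – |
| 5% | 0.3325 / 0.190 | 94.6% | 60.3% | 69.2 | 26.1% | 7.3% | 0.9% |
| 10% | 0.315 / 0.180 | 94.0% | 57.8% | 70.0 | 24.8% | 12.1% | 1.8% |
| 20% | 0.280 / 0.160 | 92.5% | 52.5% | 71.9 | 22.0% | 19.3% | 3.4% |

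**5. Unequal reclassification.**

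- f = 10% in the better arm only (0.315 v 0.20): PCS 90.3%.
- f = 10% in the worse arm only (0.35 v 0.18): PCS 97.2%.
- f = 20% in the better arm only (0.28 v 0.20): PCS 82.2%.
- No true difference (0.20 v 0.20), f = 20% in one arm only: the other arm is selected 69.7% of the time instead of 50%.

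**The case against.** The strongest reply is that the mismatches are uneven and the text carries cues. Filter thrombosis is the only clear contradiction. The imaging criteria in Section III may simply say how a DVT or PE is confirmed. Line removal or replacement counts in both places. Atrial fibrillation may be a stray example under a heading that still says thrombotic events. The first list sits under Primary Endpoint, whereas Section III appears under reporting requirements and includes items outside the composite, so the list could be taken to govern. Section IV already brings every suspected component under blinded review, and its definitions may be in adjudication documents not included here. A sensitivity analysis excluding CRRT patients is planned.

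Part of this stands. Line thrombosis is the weakest of the four, and MI is only ambiguous. The magnitude rests on assumed rates and moves patients one way only, although filter discordance runs both ways. Disagreement on stopping at 60 mostly changes enrolment: in 95%, 94% and 91% of those trials (f = 5%, 10%, 20%) both readings still choose the same arm.

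The rest does not settle the point. The heading of Section III cuts against treating it as reporting only. Reading its imaging criteria as a gloss on confirmation leaves the treated-without-imaging route unresolved. Blinded reviewers can decide whether a criterion was met but not which criterion applies. The CRRT exclusion belongs to the 60-patient analysis and does not touch the tallies that drive selection.

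**Conclusion.** The concern holds: the endpoint definitions are wrong as written and should be fixed. Four components have conflicting criteria in the current text, most plainly filter thrombosis, and nothing in the documents resolves them.

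The size is unknown because the documents give no rate for the discordant events. With equal reclassification of up to 20% of successes, the 90% guarantee still holds and the selected arm rarely reverses. The serious case is unequal reclassification. It could lower or raise the probability of correct selection, and at 20% in the better arm alone it breaks the guarantee. The documents give neither the rate nor the direction, so these figures illustrate sensitivity and do not predict bias.

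**What to change.** - Reconcile the Study Aims and Primary Endpoint lists with Section III in one governing definition table, cited from each place. State whether Section III defines the primary endpoint or only what is reported.
- Give one criterion each for filter thrombosis, DVT/PE, line thrombosis and MI. The choice is for the sponsor.
- Remove atrial fibrillation from the examples of thrombotic events. This corrects endpoint wording and says nothing about its treatment.
- Have Section IV cite the table, and add filter and other thrombosis to its named definitions.
- Apply the table to all patients, including those already enrolled, and report the alternative reading as a sensitivity analysis.

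Minimizing Selection Bias plans no efficacy comparison until 30 pairs are recruited, so the change can be made and dated without arm-level data.

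The cost is wording in the endpoint and adjudication sections plus one sensitivity analysis. Because enrolment is under way (Randomization procedures), some events already adjudicated may need re-scoring from the data already collected. Any departure from the criterion used so far must be documented as made without sight of results by arm.

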Patient Exclusion Criteria	
 • Weight under 50kg • Contraindication to anticoagulation in the opinion of the treating clinician including 
 ○ overt bleeding ○ platelet count <50,000 ○ BARC major bleeding in the past 30 days ○ GI bleeding within 3 months ○ history of intracranial hemorrhage ○ Ischemic stroke within the past 2 weeks ○ craniotomy/major neurosurgery within the past 30 days ○ cardiothoracic surgery within the past 30 days ○ intra-abdominal surgery within 30 days prior to enrollment ○ Head or spinal trauma in the last months ○ History of uncorrected cerebral aneurysm or arteriovenous malformation AVM

	
 ○ Intracranial malignancy ○ Presence of an epidural or spinal catheter ○ Recent major surgery within the last 14 days ○ Decrease in hemoglobin >3 g/dL over the last 24 hours ○ Allergic reaction to anticoagulants (e.g. Heparin Induced Thrombocytopenia) as documented in the electronic health records. Extracorporeal membrane oxygenation (ECMO) support or other mechanical circulatory support. ● Severe chronic liver dysfunction (history of portosystemic HTN, esophageal varices, or Child-Pugh class C or above or similar MELD scores), abnormality in liver function tests (AST, ALT, bilirubin) 5 times greater than upper normal limit. ● History of cirrhosis ● A history of congenital bleeding diatheses or anatomical anomaly that predisposes to hemorrhage (e.g. hemophilia, hereditary hemorrhagic telangiectasia) ● Treating physician preference for therapeutic anticoagulation ● Enrollment in other concurrent trials related to anticoagulant or antiplatelet therapy ● Existing treatment with therapeutic anticoagulation during the previous 7 days of hospitalization prior to ICU admission (e.g. for VTE, atrial fibrillation, mechanical valve, etc). ● CMO orders prior to enrollment.
--	--

II. Study Procedures

- a. Screening procedures
- b. Randomization
- c. Study intervention
- d. Study Assessments and Activities

Screening procedures	All patients in participating CUIMC ICUs will be screened by the study team. Study eligibility criteria (described above) will be implemented to identify the modified intention-to-treat cohort.

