	
 • ISTH major bleeding: 1: Fatal bleeding, and/or 2. Symptomatic bleeding in a critical area or organ, such as intracranial, intraspinal, intraocular, retroperitoneal, intraarticular or pericardial, or intramuscular with compartment syndrome, and/or 3. Bleeding causing a fall in hemoglobin level of 2 g/dL (1.24 mmol/L) or more, or leading to transfusion of two or more units of whole blood or red cells. • TIMI major bleeding: Any intracranial bleeding (excluding microhemorrhages ≤ 10 mm evident only on gradient-echo MRI), or Clinically overt signs of hemorrhage associated with a drop in hemoglobin of ≥ 5 g/dL, or Fatal bleeding (bleeding that directly results in death within 7 d
--	--

IV. Event Adjudication

A clinical events committee will be formed for adjudication of clinical endpoints. Suspected components of the primary endpoint as well as the secondary endpoints, including the bleeding endpoint as documented in case report forms will be adjudicated based on pre-defined clinical definitions of venous thromboembolism, myocardial infarction, ischemic stroke, acute limb ischemia, clinically-actionable line thrombosis, and major bleeding. All suspected events will be independently reviewed by two physicians blinded to randomized group assignment. If there is disagreement on whether an endpoint event has occurred, the case will be reviewed by the clinical events committee for adjudication.

V. Safety Monitoring Plan

All events outlined above will be reported to the Clinical Events Committee (CEC) and Data and Safety Monitoring Board (DSMB) and reviewed on a regular basis. The DSMB may request additional information as needed. Based on safety data, the DSMB may recommend to the Study Chairman to stop or otherwise modify the study. The Study Chairman will make the final decision after weighing the recommendation of the DSMB whether the study should then be stopped, modified or continued without change. The DSMB procedures will be described in the DSMB Charter.

VI. Risk/Benefit Analysis

Include research related risks and potential benefits (if any).

There is equipoise for the antithrombotic treatment intensity in patients with severe COVID-19. The table below summarizes the potential benefits and risks of intermediate-dose vs. prophylactic dose anticoagulation.

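### The endpoint table gives atrial fibrillation as an example of a thrombotic event, in conflict with the primary endpoint definition, so a survivor anticoagulated for it with no thrombus can be scored a failure

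*Combined protocol and SAP*

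**What the plan says.** Success on the primary endpoint is "Composite of being alive and without clinically-relevant venous or arterial thrombotic events at discharge from ICU" (Primary Endpoint). One listed event is enough for failure: "Clinically relevant venous or arterial thrombotic events will all be adjudicated and are defined as any of the following" (Study Aims and Objectives; repeated under Primary Endpoint). The last item on that list is "Other thrombotic events requiring anticoagulation (e.g., intracardiac thrombosis").

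The table in III. Endpoint Definition, a) Endpoint Reporting Requirements, has a row with the same name, "Other thrombotic events requiring anticoagulation". Its whole content is "For example atrial fibrillation, left ventricular thrombus, right ventricular thrombus, etc". The row does not ask for a thrombus, an embolus, imaging or new onset.

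AF appears in two other places, each time as a reason to anticoagulate:

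- Study intervention, in the daily dose assessment: "development of another indication for anticoagulation such as new-onset atrial fibrillation".
- Patient Exclusion Criteria: "Existing treatment with therapeutic anticoagulation during the previous 7 days of hospitalization prior to ICU admission (e.g. for VTE, atrial fibrillation, mechanical valve, etc"). This removes baseline AF only where it was already being treated with therapeutic anticoagulation.

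IV. Event Adjudication says that suspected components are "adjudicated based on pre-defined clinical definitions of venous thromboembolism, myocardial infarction, ischemic stroke, acute limb ischemia, clinically-actionable line thrombosis, and major bleeding". The residual component is not in that list.

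**The concern.** AF is an arrhythmia and a reason to anticoagulate. It is not itself a venous or arterial thrombosis. Under the table row, a patient who develops AF, is anticoagulated for it, has no clot found and leaves the ICU alive can be counted as a poor outcome, although the endpoint is meant to capture survival free of thrombosis.

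Whether AF requires anticoagulation is decided at the bedside. There the arm is evident, because rooms are designated by dose and the regimens differ visibly. A treatment decision can therefore help to create a primary event.

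Each patient's good or poor score feeds the success tallies, and a lead of 4 selects the arm. The same classification carries into the odds ratio from the first 60 patients, the likelihood-ratio evidence and the component-level secondary endpoints.

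**Working it through.** **1. The texts side by side.**

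| Place | How AF or the residual component is treated |
|---|---|
| Study Aims and Objectives; Primary Endpoint | Component of the primary endpoint; only example is intracardiac thrombosis |
| III. Endpoint Definition, table | Same component name; AF is the first example, beside two ventricular thrombi |
| II. Study Procedures, Study intervention | New-onset AF is an indication for anticoagulation |
| IV. Event Adjudication | Residual component missing from the listed definitions |

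The table row is the only text that expands on this component, and nothing elsewhere overrides it. The two physicians who review each event are blinded, but for this component the documents point them to no other definition.

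**2. Reproducing the plan's figures.** The inputs are from section VIII: p1 = 0.35 and p2 = 0.20, no decision before 60 patients (30 per arm), stop at a lead of 4 or more, truncation at 100 patients (50 pairs). The exact calculation takes two independent Binomial(30, p) tallies and stops if they differ by 4 or more. Otherwise it adds one pair at a time up to 50 pairs, with

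- P(lead +1) = p1(1 − p2)
- P(lead −1) = p2(1 − p1)

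The larger tally wins at truncation, and ties are split 50:50. For Scenario 1 of Table 1:

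| | Table 1 | Exact |
|---|---|---|
| Probability of correct selection (PCS) | 95.1% | 95.2% |
| Expected sample size | 68.4 | 68.4 |
| P(stop at 60) | 62.6% | 62.6% |
| P(truncation) | 10.2% | 10.4% |

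The odds ratio is (0.35/0.65)/(0.20/0.80) = 2.15. The plan's figures reproduce.

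**3. Effect of counting AF, equal in both arms.** Two assumptions are needed, because the documents settle neither:

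- a share *a* of would-be successes in each arm has AF that leads to anticoagulation;
- 0.35 and 0.20 are the success rates with AF *not* counted as failure.

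Counting AF as failure then gives success rates 0.35(1 − *a*) and 0.20(1 − *a*). The expected lead after 30 per arm is 30 × 0.15 × (1 − *a*).

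| *a* | Success rates | Odds ratio | Expected lead at 60 | P(stop at 60) | PCS |
|---|---|---|---|---|---|
| 0 | 0.350, 0.200 | 2.15 | 4.5 | 62.6% | 95.2% |
| 5% | 0.333, 0.190 | 2.12 | 4.3 | 60.3% | 94.6% |
| 10% | 0.315, 0.180 | 2.09 | 4.05 | 57.8% | 94.0% |
| 15% | 0.298, 0.170 | 2.07 | 3.8 | 55.2% | 93.3% |
| 20% | 0.280, 0.160 | 2.04 | 3.6 | 52.5% | 92.5% |

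At *a* = 10%, the expected number reclassified per 30 patients is 30 × 0.35 × 0.10 = 1.05 in the better arm and 30 × 0.20 × 0.10 = 0.6 in the other. PCS reaches 90% only at *a* of about 34%.

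**4. Unequal rates.**

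| *a* in better arm | *a* in worse arm | PCS |
|---|---|---|
| 10% | 5% | 92.3% |
| 15% | 5% | 89.2% |
| 5% | 10% | 95.9% |
| 5% | 15% | 96.9% |

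The documents give no basis for expecting either direction.

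**The case against.** The strongest reply is that the documents are ambiguous and do not clearly make AF a failure. The row label asks for a thrombotic event that also requires anticoagulation, and AF without a clot fits the example but not the label. The table is introduced as a list of reportable endpoints and also holds kidney injury and bleeding, which are not primary components. Blinded reviewers might set AF aside. Study intervention governs dosing, not scoring, so calling AF an indication there does not settle how it is scored.

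Much of this stands. A reader might infer that any survivor with an arrhythmia is scored as a failure. The documents do not support that: only AF that leads to anticoagulation could qualify, and the wording permits that scoring without establishing that it is applied. The real conflict is between the table and the two statements of the primary endpoint; Study intervention is supporting evidence. But an adjudicator who disregards AF must depart from the row, and if some apply it and others do not, scoring is inconsistent.

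The reply is also right on size. If 0.35 and 0.20 were set for the endpoint with AF counted, the design loses nothing. A reader might note that the diluted odds ratios lie below the 2.15 preference-zone boundary and infer that the guarantee fails. It does not at equal rates up to 20%, where PCS stays at 92.5% or more. Nor do the documents support a bias towards a particular arm. Dependence on a treatment decision is not unique to AF either: treated venous thrombosis and line or filter thrombosis needing escalation share it. What sets AF apart is that no thrombosis is involved.

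**Conclusion.** The inconsistency is real and should be corrected. It concerns what the primary endpoint measures: as written, a clot-free survivor anticoagulated for AF can lower an arm's success tally, and the adjudication section supplies no definition that would prevent it.

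The effect on the selection design is modest if AF is balanced: PCS of 94.6% to 92.5% for assumed rates of 5% to 20%, against 95.2% without AF failures and a 90% target. With the unequal rates examined, PCS runs from 89.2% to 96.9%, and only the 15% versus 5% case falls below target. All these figures rest on an assumed AF rate and on 0.35 and 0.20 excluding AF failures. They show sensitivity and do not predict what will happen in this trial. In a single trial, one or two such patients in one arm would still move the lead by one or two of the 4 needed.

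**What to change.** Reconcile the table in III. Endpoint Definition with Study Aims and Objectives and Primary Endpoint:

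- Delete AF from the row, so that the component requires a documented thrombus, such as the left or right ventricular thrombus already listed there.
- Add this component to the definitions named in IV. Event Adjudication.
- Record AF separately, as a non-endpoint reason for a change in anticoagulation.
- Recruitment had already begun under this version, so re-adjudicate any event recorded on AF alone. Do this blinded to arm and before the tallies are compared, because unblinded or later reclassification could itself decide the selection.

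The change is to endpoint classification only and leaves patient management untouched. The cost is a wording change, a revised adjudication form, blinded re-review of any AF-only events, and slightly fewer primary events. No new data are needed.
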